Health
Sydney
Local Health District

PMBC Sleep Program

PROTOCOL NUMBER: VERSION 1.0 (APRIL 2018)

ADMINISTRATIVE INFORMATION

DATA CATEGORY	INFORMATION
Scientific Title	A pilot evaluation of sleep program to improve sleep quality in male psychiatric HDU inpatients
Public Title	PMBC sleep program
Date of Registration	TBC
Primary registry and trial identification number	TBC
Date of Registration in primary registry	TBC
Secondary identification numbers	TBC
Source of monetary or material support	Fully funded by the Sydney Local Health District (\$50,000)
Primary Sponsor	Sydney Local Health District
Contact for public queries	[name] [name], [contact]
Contact for scientific queries	[name] [name], [contact]
Countries of recruitment	Australia
Health condition(s) or problem(s) studied	Inpatient male HDU psychiatric patients of all diagnoses
Intervention(s)	Ward-based initiatives and activity groups
Comparator	Routine male inpatient psychiatric HDU patients' length of stay with and without therapy; previous admissions
Inclusion criteria	Males aged 18+ years. Able to give informed written consent. Literacy in English. Inpatient at PMBC psychiatric Male High Dependency Unit (HDU).
Exclusion criteria	Current substance dependence. Severely unwell such that not able to give consent or tolerating participation in group sessions. Severe cognitive impairment or thought disorder. Not

	proficient in English. Recent transmeridian (>2 time zones) travel (within last 1 month).
Study type	Interventional; Allocation: nonrandomized; Masking: none (open label trial)
Primary Purpose	Pilot Study, Feasibility Study
Date of first enrolment	May 2018
Target sample size	N/A (Pilot study, rolling recruitment)
Recruitment status	Recruitment not yet commenced.
Primary outcomes	Actigraphic changes in sleep duration (Respironics Actigraphy data)
Key secondary outcomes	
Sleep quality (weekly Visual Analogue Scale (VAS) and Pittsburgh Sleep Quality Index measured at start and end of study)
 
Self-report duration
 
Length of stay in HDU
 
Use of as needed (PRN) sedatives for sleep
 
Sleep efficiency (actigraphy)
 
Engagement in group
 
Autonomy
 
Participant satisfaction

Protocol Version:	Version 1.0, April 2018
Revision Chronology	Version 1.0, April 2018: Original.
Protocol Amendment Number	0
Authors	[name] BE(Hons) BCom MBBS, [name] BPsych(Hons), [name] MBBS PhD

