In conclusion, scientific research suggests that in the clinical setting, actigraphy is reliable for evaluating sleep patterns in patients with insomnia, for studying the effect of treatments designed to improve sleep, in the diagnosis of circadian rhythm disorders (including shift work), and in evaluating sleep in individuals who are less likely to tolerate PSG, such as inpatient psychiatric patients. While actigraphy has been used in research studies for many years, it is only recently that the methodological issues have been systematically addressed in clinical research and practice. With those issues addressed, the use of actigraphy is now being applied to clinical practice. (Ancoli-Israel et al, 2003).

STUDY OBJECTIVES

Primary Objective

To evaluate the effect of the Sleep Program on duration of admission in HDU (compared to controls) and sleep duration (Actigraphy data), in male psychiatric HDU inpatient participants.

Secondary objectives

1. Sleep quality - improvement in the Pittsburgh Sleep Quality Index
2. Sleep efficiency- percentage time in bed vs percentage time asleep
3. To test the engagement (tolerability and practicality) with a structured Stimulus Control Therapy Program
4. Impact on use of as needed (PRN) hypnotics
5. To describe the characteristic of sleep, activity and light exposure of patients in a high dependency psychiatric unit using wrist actigraphy.

Hypotheses

- We hypothesise that a structured stimulus control program for sleep will shorten duration of admission at psychiatric HDU.
- There will be an improvement in the sleep duration and efficiency
- There will be an improvement in the quality of sleep via a reduction of the self-rated Pittsburgh Sleep Quality Index score, measured at the beginning and end of the study.
- Participants in the Bright Light Study will engage in a structured stimulus control therapy program and it will be well-tolerated.

STUDY DESIGN

Design, Study Groups, Number of Participants

This is a pilot study for a complex intervention and we do not know the effect of variance. We seek to test our methodology, exterminate recruitment and retention rates, feasibility and finally, determine the sample size. We also seek to highlight any issues with acceptability, compliance, and delivery of our interventions.

Number of centres

Single-centre, at [name] Centre, male High Dependency (psychiatric) Unit

Duration

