We foresee the duration of the pilot study of approximately 6 months. Recruitment is on a continuous basis; with approximately 4-6 patients recruited at any given time.

Initial recruitment phase is one week, where patients are identified (see recruitment procedures).

Initial recruitment will be 4-6 patients. The patient is recruited for as long as they are an inpatient at the HDU and discontinued at their discharge (or at their request). Subsequent patients are then recruited in the same process to maintain 4-6 patients at any given time in the program for the duration of the pilot study.

PARTICIPANTS

Inclusion Criteria

1. Males 18+ years.
2. Inpatient in psychiatric Male HDU at PMBC
3. Willingness to give informed written consent and willingness to participate to and comply with the study.
4. Literacy in English.

Exclusion Criteria

1. Current substance dependence.
2. Severe cognitive impairment or thought disorder that does not allow participants to consent or follow treatment instructions.
3. Recent time-zone travel (within last 1 month).

STUDY OUTLINE

Interventions

The intervention is an integrated Sleep Program. It comprises of two main components, thrice weekly group sessions and ward environmental initiatives. The overarching aim is to improve sleep through;

1. **Increase daytime activity**, particularly in the morning if possible, with use of the balcony and outdoor areas. It has the ultimate aim of establishing routine. Many patients in a hospital setting experience a lack of activity. For example, patients may spend a lot of time in bed watching TV or napping throughout the day.
2. **Setting regular rhythms** – enhanced light/dark exposure to stabilize circadian rhythms.
3. **Stimulus control and relaxation** – simple breathing techniques, relaxing music through headphones, relaxation on bean bags
4. Encourage patient-driven management through **psychoeducation**, ongoing sleep quality monitoring and feedback, and driving behavioural change in the ward milieu.

The total duration of a patient’s participation in the Program is flexible. However, we consider a 2-week duration as the minimum dose.

Ward environmental initiatives

A number of initiatives are adopted, these are summarised below. They are specific to the participants of the study. Bean bag and visual cues (ward posters) are made available to the participants in their own rooms; while headphones are pre-existing equipment available to all patients in the HDU.

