- familial distress
- harm to any member of a vulnerable population
- reputational harm

Informed Consent Process

There is a one-stage consent process to entry into the study. The Senior occupational therapist, [name] (investigator in this study) will introduce the study and discuss the main aspects to potential eligible participants in person in the first instance to reduce medical-patient power imbalance.

Participants will receive the study information sheets in hard copy. Research clinicians will discuss the study with participants in light of the information provided to them. The research clinician will obtain written content from patients willing to participate.

A potential participant has one week to consider their participation; however, they may defer that decision up until two weeks prior to their expected discharge date from the HDU - given a meaningful study period is defined as a minimum of two weeks of participation.

Enrolment Procedure

The participant will be enrolled into the study after the informed consent process has been completed and the participant has met all inclusion criteria and none of the exclusion criteria.

Participants need to be inpatient at HDU North (male) in PMBC, Royal Prince Alfred Hospital.

Participants are first identified as potential (candidate) participant by medical/OT/SW/RN from Multi-Disciplinary Team (MDT) meeting, satisfying inclusion and exclusion criteria.

The participant will receive a study enrolment number (Participant ID number), and this will be documented in secure and confidential register, as well as in the medical records.

Capacity

Potential (candidate) participants are clinically assessed for the ability to understand and capacity to give consent. The consultant in the treating team must deem the candidate participant as having capacity to consent; and this must be a consensus impression by the rest of the MDT. Further, it must be verifiable by demonstrated understanding and engagement with the Sleep Program. Mental state is monitored on an ongoing basis as per standard care. In cases where a participant deteriorates or loses capacity to consent and participate altogether: their involvement in the study will cease. This is outlined under *Early Terminations*.

Randomisation Procedure

Not applicable

Adverse Event Reporting

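### The length-of-stay comparison sets programme men selected on capacity and other entry criteria against routine HDU men with no stated eligibility restriction

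*Protocol*

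**What the plan says.** The Comparator row of the Administrative Information table names routine male psychiatric HDU inpatients' "length of stay with and without therapy; previous admissions". No section adds an eligibility filter, matching or a severity restriction for these stays. The same table describes the study as non-randomised and open label.

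The comparator serves a stated objective. Under Study Objectives, the Primary Objective begins "To evaluate the effect of the Sleep Program on duration of admission in HDU (compared to controls", and the first item under Hypotheses is that "a structured stimulus control program for sleep will shorten duration of admission at psychiatric HDU". The Administrative Information table lists HDU length of stay as a key secondary outcome instead; the present point applies under either label.

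Programme men pass several filters. The Exclusion criteria row of the table removes men who are "Severely unwell such that not able to give consent or tolerating participation in group sessions". That row and the Exclusion Criteria under Participants both list "Current substance dependence" and severe cognitive impairment or thought disorder. English is required in both places. Under Capacity, "The consultant in the treating team must deem the candidate participant as having capacity to consent", and the multidisciplinary team must agree.

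**The concern.** Capacity, severity of illness and substance dependence are plausible determinants of how long a man stays in an HDU. If they restrict one side of the comparison and not the other, the groups can differ in expected stay before the programme does anything. A difference would then be read as a programme effect, or a real effect could be hidden.

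Pilot status does not remove the problem. The Background says the pilot is meant to determine the programme's effect and the variance of that effect, so a confounded length-of-stay contrast could carry into later decisions. The actigraphic sleep-duration outcome is not touched by this point.

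**Working it through.** The Protocol gives no length-of-stay mean, standard deviation, target difference or sample size, so there is no figure of its own to reproduce. The check sets the texts side by side and then illustrates the size.

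**1. Who is on each side**

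| Criterion | Programme men | Routine comparator stays |
|---|---|---|
| Capacity to consent | Required (Capacity) | Not stated |
| Well enough to consent and tolerate groups | Required (Administrative Information) | Not stated |
| No current substance dependence | Required (Administrative Information; Participants) | Not stated |
| No severe cognitive impairment or thought disorder | Required (same places) | Not stated |
| English | Required (same places) | Not stated |
| Removed from analysis after loss of capacity or of ability to take part | Yes (Early Termination) | Not stated |

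**2. Whether anything corrects the imbalance**

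Allocation is not randomised. The Statistical Analysis Plan section of the Protocol names only within-person differences of means and expects too few data for regression. Nothing there adjusts a between-men comparison.

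**3. Illustration as a ratio, with no programme effect**

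Let q be the share of routine men who would fail the criteria, and k their mean stay divided by that of eligible men. With eligible mean E, the routine mean is (1 - q)E + qkE. The apparent ratio, programme over routine, is R = 1/(1 - q + qk). The values of q and k and a routine mean of 21 days are assumptions.

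- q = 0.3, k = 1.5: R = 1/1.15 = 0.870, a change of -13%, or 21 x (0.870 - 1) = -2.7 days.
- q = 0.5, k = 2: R = 1/1.5 = 0.667, a change of -33%, or -7.0 days.
- q = 0.3, k = 0.7: R = 1/0.91 = 1.099, a change of +10%, or +2.1 days.

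**4. Illustration in days**

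If a share s of routine men would fail the criteria and stay d days longer on average, then routine mean minus eligible mean = s x d. With s from 0.2 to 0.6 and d from 3 to 14 days (both assumed), this runs from 0.2 x 3 = 0.6 to 0.6 x 14 = 8.4 days; s = 0.4 and d = 7 give 2.8 days. For scale only, the one length-of-stay difference cited in the Background is 3.67 days. Matching it at s = 0.4 would need d = 3.67/0.4 = 9.2 days.

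**5. A separate selection that can pull the other way**

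The Informed Consent Process section defines a meaningful study period as at least two weeks. If only stays of 14 days or more entered the programme group, and stays were exponential with mean m (an assumption), their mean would be m + 14, so 14 days above the unrestricted mean. This is a different mechanism from the eligibility criteria, but it shows that the net sign is open.

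**The case against.** The strongest case on the other side has five parts.

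- **The comparator has a second element.** A reader might infer that every comparator stay belongs to other, unselected men. The text does not support that. Previous admissions may mean participants' own earlier stays, which would fit the within-person analysis, and for that element the contrast between different men does not arise. This stands. However, those earlier stays are not stated to meet the criteria either, and the routine-patient element remains.
- **The absence of a filter is silence, not a statement.** The comparator is one row in a table, and a separate analysis plan could define it further. But the row does name routine HDU patients, and who the controls are is a design choice this Protocol makes. Followed as written, it gives an unrestricted comparator.
- **Severity changes within a stay.** Recruitment is continuous, and a man may defer his decision until two weeks before expected discharge. A man too unwell at admission may qualify later in the same stay, so severely ill, long-stay men are not necessarily missing from the programme group. This stands: a fixed q and k illustrate the problem but do not model the process. Substance dependence and English proficiency are more stable, though they are not measures of severity.
- **The size rests on no document figure.** This also stands. The 3.67 days compares east-facing with west-facing rooms in an inpatient hospital setting; it is neither an HDU figure nor a target effect for this programme.
- **The pilot is mainly descriptive.** The Protocol specifies no between-group test and ties sample size to actigraphy. Even so, the Primary Objective and the first hypothesis state a comparative claim about stay, and a descriptive analysis cannot support it.

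**Conclusion.** The point holds in a limited form. As written, the length-of-stay part of the Primary Objective contrasts men selected on capacity, group tolerance, English, substance dependence and cognition or thought disorder with routine men for whom no such restriction is stated. Nothing in the Protocol adjusts for this, so the contrast is confounded.

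The non-comparability follows from the text and needs no assumed number. The direction and size of the bias do not. The illustrative values of -7.0, -2.7 and +2.1 days, and 0.6 to 8.4 days in the other form, depend wholly on assumed shares, assumed differences in stay and, in the first form, an assumed 21-day mean. A reader might infer that the design is tilted towards showing a shorter stay; the document gives no length of stay by severity or dependence and does not support that. The change should be made, but the main actigraphic outcome does not depend on it.

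**What to change.** Restrict the routine comparator to HDU stays that meet the criteria readable from the medical record: no current substance dependence, English proficiency, no severe cognitive impairment or thought disorder, and capacity where it is noted at any point in the stay. Report stays where these cannot be read as a separate group. Say whether previous admissions means participants' own earlier stays and, if so, whether those stays must meet the same criteria.

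State the limits alongside. Group tolerance cannot be matched in men who were never offered groups. The Capacity section also asks for understanding shown through engagement with the programme, which a non-participant's record cannot show. The two-week participation rule and the exclusion of early terminations need their own handling; a criteria-matched comparator does not resolve them.

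If individual records are not available (the Digital Data section mentions only aggregate length-of-stay data), delete the comparison with controls from the Primary Objective, recast the length-of-stay hypothesis as exploratory, and report length of stay descriptively with no effect claim.

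The main fix costs a record check and a smaller comparator group. The fallback is a wording change only. The Administrative Information table says recruitment has not begun, so on that footing either could be made before data exist.

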During the past week,.....	33
Sleep Diary	34
Visual Analogue Scale : Sleep Quality.....	35
Ward Poster : A Good Night’s Sleep	36
Patient Autonomy and Satisfaction Survey	37

BACKGROUND

Disease Background and Rationale

Disturbances of sleep are prominent and have a fundamental impact on the course of psychiatric disorders (Benca et al., 1992). Depending on the severity of illness, sleep disturbance occurs in 30 to 80% of patients with schizophrenia, and is associated with positive and negative symptoms, cognitive deficits, poorer outcome, and impaired quality of life. (Chan et al, 2017) Conversely, sleep disturbance is common to patients admitted at acute crisis to a psychiatric hospital. Approximately eight out of 10 patients report clinically significant insomnia. (Haynes et al, 2011) In fact, most medical and psychiatric disorders are associated with disturbed sleep. This is evident by the difficulty initiating and maintaining sleep in most psychiatric disorders and fragmented sleep seen in many medical disorders (Cauter et al, 1991). In addition, patients often take medications which penetrate the CNS and have the potential to alter sleep. Aside from prescription and over-the-counter medications, and herbal preparations, attention must be paid to the amount and timing of alcohol and caffeine consumption. (Jobert et al, 2012)

The assessment of sleep disturbance includes face-to-face interview, self-report questionnaire, sleep diary, actigraphy, and polysomnography (PSG). PSG is an objective method to derive quantitative sleep measures and records electroencephalogram (EEG), electro-oculo-gram (EOG) and electromyogram (EMG). (Chan et al, 2017) Compared to healthy controls, patients with schizophrenia were shown to have significantly lower Total Sleep Time (TST) and Sleep Efficiency (SE), longer Sleep Onset Latency (SOL) and Total Awake Time (TAT). (Chan et al, 2017)

The treatment of sleep disturbances has shown to reduce psychological distress and psychotic experiences including delusions and hallucinations (Freeman et al. 2015; Freeman et al., 2017; Myers et al., 2011). Presently, hypnotic pharmacotherapy remains the mainstay management for sleep disturbances in inpatient and outpatient settings. (Buysse 2013, Winkler A 2009)

Research has shown that the sleep-wake cycle is strongly linked to the environment (Czeisler et al. 1980; Rea et al. 2008) and disruptions to this cycle may result in sleep disturbances as well as negative cognitive and psychological consequences (Lane & East, 2008). Hospital environments tend to report low lighting levels which may distort the normal circadian sleep-wake rhythms. Bendetti et al. (2001) assessed an inpatient hospital setting over 2 years and reported an average reduction of 3.67 days in admission in those rooms facing east compared to rooms facing the west. The addition of increased outdoor activities and light glasses in the current study increases exposure to light which can assist in stabilising the circadian rhythm.

Moreover, evidence-based interventions such as cognitive behavioural therapy for insomnia (CBT-I) has shown promising results within clinical settings involving patients with schizophrenia, psychosis and patients in acute care (Freeman et al., 2015; Sheaves et al., 2017).

This study has 2 goals. The first goal is a pilot study of an integrated, ward-based behavioural therapy (the Sleep Program) to improve the quality sleep of psychiatric inpatients in order to determine its effect, variance of effect and feasibility. The second is to describe the characteristic of sleep, activity and light exposure of patients in a high dependency psychiatric unit using wrist actigraphy.

Actigraphy

Wrist actigraphy has been used to measure sleep rhythms for over 25 years (Kripke et al., 1978, Mullaney et al., 1980). Actigraphs are watch like devices generally placed on the wrist to record movement. Most are based on weighted activity (accelerometry) counts in a given epoch of time which detect sleep/wake according to threshold values. Activity data is then processed and analysed by computer software programs and specialized algorithms are used to estimate sleep and activity parameters. The analysis utilises algorithms which have been developed, compared and validated since the original use of actigraphs (Cole et al., 1992, Sadeh et al., 1994, Jean-Louis et al., 2001, Tryon, 2005, Kripke et al., 2010). As actigraphic devices have evolved, so too has the number of channels used to collect additional data streams (light, event markers, subjective scores, and off-wrist capacitance). (Ancoli-Israel et al, 2003)

Polysomnography (PSG) is the gold standard technology for assessing sleep. It is objective, but it is also expensive and limited to just a few nights of data collection in a lab setting which would impede its ability to document sleep problems in a inpatient psychiatric ward. The polysomnography testing process can also interfere with sleep, especially on the first night. Benefits of actigraphy over traditional polysomnography is that you can record continuously for 24 hours per day for days, weeks or longer. Conversely, patient-reported sleep questionnaires are low cost, can be used for multiple nights, and likely do not interfere with sleep. However, they are imprecise and subjective. The subjective nature of questionnaires can be useful if the subjective sleep assessment is the therapy target but can be a problem if you want to detect changes in small Phase 2 or pilot studies. Monk et al. compared both actigraphs and sleep diaries to PSG during space flight. Predicted values of actigraphy were clearly superior to those of diaries for sleep onset and offset, sleep duration, and sleep efficiency.

Actigraphy has been used to investigate movement and sleep disturbance in psychiatric patients. Dursun et al. conducted a descriptive study of wrist actigraphy estimation of sleep in outpatients with schizophrenia prescribed risperidone compared to those on “typical” antipsychotics, and to normal controls. They found a greater degree of nighttime wrist movement (i.e., higher movement index) in patients on a typical antipsychotic compared to those on risperidone. Lemke et al. used wrist actigraphy to estimate mean activity levels in psychiatric unit inpatients with major depressive disorder (evidence level 4C-b).¹⁵³ They found that subjects whose Pittsburgh Sleep Quality Index indicated poor sleep had higher mean nighttime motor activity levels than those who reported good sleep. In addition, subjects with fewer depressive symptoms had lower mean nighttime motor activity levels than those with greater depressive symptomatology.

In conclusion, scientific research suggests that in the clinical setting, actigraphy is reliable for evaluating sleep patterns in patients with insomnia, for studying the effect of treatments designed to improve sleep, in the diagnosis of circadian rhythm disorders (including shift work), and in evaluating sleep in individuals who are less likely to tolerate PSG, such as inpatient psychiatric patients. While actigraphy has been used in research studies for many years, it is only recently that the methodological issues have been systematically addressed in clinical research and practice. With those issues addressed, the use of actigraphy is now being applied to clinical practice. (Ancoli-Israel et al, 2003).

STUDY OBJECTIVES

Primary Objective

To evaluate the effect of the Sleep Program on duration of admission in HDU (compared to controls) and sleep duration (Actigraphy data), in male psychiatric HDU inpatient participants.

Secondary objectives

1. Sleep quality - improvement in the Pittsburgh Sleep Quality Index
2. Sleep efficiency- percentage time in bed vs percentage time asleep
3. To test the engagement (tolerability and practicality) with a structured Stimulus Control Therapy Program
4. Impact on use of as needed (PRN) hypnotics
5. To describe the characteristic of sleep, activity and light exposure of patients in a high dependency psychiatric unit using wrist actigraphy.

Hypotheses

- We hypothesise that a structured stimulus control program for sleep will shorten duration of admission at psychiatric HDU.
- There will be an improvement in the sleep duration and efficiency
- There will be an improvement in the quality of sleep via a reduction of the self-rated Pittsburgh Sleep Quality Index score, measured at the beginning and end of the study.
- Participants in the Bright Light Study will engage in a structured stimulus control therapy program and it will be well-tolerated.

STUDY DESIGN

Design, Study Groups, Number of Participants

This is a pilot study for a complex intervention and we do not know the effect of variance. We seek to test our methodology, exterminate recruitment and retention rates, feasibility and finally, determine the sample size. We also seek to highlight any issues with acceptability, compliance, and delivery of our interventions.

Number of centres

Single-centre, at [name] Centre, male High Dependency (psychiatric) Unit

Duration

We foresee the duration of the pilot study of approximately 6 months. Recruitment is on a continuous basis; with approximately 4-6 patients recruited at any given time.

Initial recruitment phase is one week, where patients are identified (see recruitment procedures).

Initial recruitment will be 4-6 patients. The patient is recruited for as long as they are an inpatient at the HDU and discontinued at their discharge (or at their request). Subsequent patients are then recruited in the same process to maintain 4-6 patients at any given time in the program for the duration of the pilot study.

PARTICIPANTS

Inclusion Criteria

1. Males 18+ years.
2. Inpatient in psychiatric Male HDU at PMBC
3. Willingness to give informed written consent and willingness to participate to and comply with the study.
4. Literacy in English.

Exclusion Criteria

1. Current substance dependence.
2. Severe cognitive impairment or thought disorder that does not allow participants to consent or follow treatment instructions.
3. Recent time-zone travel (within last 1 month).

STUDY OUTLINE

Interventions

The intervention is an integrated Sleep Program. It comprises of two main components, thrice weekly group sessions and ward environmental initiatives. The overarching aim is to improve sleep through;

1. **Increase daytime activity**, particularly in the morning if possible, with use of the balcony and outdoor areas. It has the ultimate aim of establishing routine. Many patients in a hospital setting experience a lack of activity. For example, patients may spend a lot of time in bed watching TV or napping throughout the day.
2. **Setting regular rhythms** – enhanced light/dark exposure to stabilize circadian rhythms.
3. **Stimulus control and relaxation** – simple breathing techniques, relaxing music through headphones, relaxation on bean bags
4. Encourage patient-driven management through **psychoeducation**, ongoing sleep quality monitoring and feedback, and driving behavioural change in the ward milieu.

The total duration of a patient’s participation in the Program is flexible. However, we consider a 2-week duration as the minimum dose.

Ward environmental initiatives

A number of initiatives are adopted, these are summarised below. They are specific to the participants of the study. Bean bag and visual cues (ward posters) are made available to the participants in their own rooms; while headphones are pre-existing equipment available to all patients in the HDU.

	Ward environmental initiatives
Stimulus Control Therapy	
 • Consistent wake time at 7am encouraged by ward staff • Beanbags: an alternate place to sit other than the bed
Sleep Psycho-education	
 • Visual cues regarding specific sleep hygiene strategies around patient room and ward area. • Reinforcement, encouragement and further psychoeducation provided by nursing staff
Increased light exposure (regulating circadian rhythm)	
 • Using available open spaces wherever possible enhanced with early morning Retimer™ blue-green light goggles for those with sleep-phase delay
Relaxation	
 • Calming music during wind down • Quiet space with dim lights and beanbags

Activity Groups

Each participant will be invited to participate in thrice-per-week, 30-minute workshops in the program, which aim to provide psychoeducation about sleep, debriefing and sleep-promotion related

activities. It is also aimed at increasing daytime activity and enforcing a regular circadian rhythm. This is conducted on a repeated weekly cycle as outlined below. These sessions will take place on the outdoor area of the HDU (the balcony) where possible such that participants will receive continuous daylight exposure during these sessions. Each session will take place in mid-morning to lunchtime.

Session 1

Session 1 are on Mondays. They are facilitated by a senior Occupational Therapist and a peer-support worker and is designed to instil a routine of activity (via a Cooking group). Initial consenting and program information will be provided to a patient who is commencing. As well, actigraph watch and sleep diary will be provided to the commencing participant, allowing for ongoing record and feedback of their sleep parameters throughout their time in the program. Qualitative feedback regarding sleep will be collected during these sessions.

Session 2

Second sessions are held on Wednesdays, on the balcony of the HDU. They are facilitated by two psychiatry registrars. Prior to the sessions, participants' actigraph watches are collected and sleep data analysed by the research assistant. A visual representation of sleep duration and activity for each patient will be printed prior to the session and given to the registrars, and printouts are identifiable only by participant IDs.

These sessions are held as a mini picnic with healthy snacks. During these sessions, printouts will be discussed individually with participants, especially with respect to their self-evaluation in their Sleep Diaries. This aims to increase insight and empower the participants to take a proactive role in their management.

As a group, the registrars will give further psychoeducation about sleep, with a focus on sleep hygiene, and addressing specific stimuli which affect sleep.

Wednesday sessions are also repeated in a weekly cycle. Patients in their initial and final weeks of the program will be asked to complete the Pittsburgh Sleep Quality Index, modified to reflect the quality of sleep within one week.

Session 3

Session three are held on Fridays and are repeated on a weekly basis. It is split into two components. Firstly, the morning session is in the form of a breakfast barbeque – which is open to the entire ward to participate. Facilitators of sessions 1 and 2 are able to join. This session is an informal way for participants and clinicians to freely exchange ideas and feedback, as well as to reinforce sleep psychoeducation provided in earlier sessions.

Secondly, there will be a booster session on Friday evenings, which is self-directed by the participants and is optional. It entails participants making use of the ward measures made available to them – to enhance relaxation and stimulus control.

Summary table of sessions

Session	Day and time	Content	Measurement tools	
			Sleep diary	Actigraphy
1	Monday 11:30am – 12pm	
 • Cooking group • Preliminary psychoeducation • Program information and obtaining consent • Providing actigraph watch and diary for participant 	X	X
	Tuesday	Nil active intervention for Day 2 participants complete diary +/- nurse Day8 participants - maintain stimulus control and am light goggles	X	X
2	Wednesday (Pre- session)	
 • Collecting watches + analysing actigraphy 	X	X
	Wednesday 11:30am – 12pm	
 • Outdoor session with snacks • Psychoeducation about • Stimulus Control Therapy, Sleep Hygiene • Present sleep results • Administer PSQI and one-item Sleep Quality measure (start and terminating session only) 		
	Thursday		X	X
3	Friday AM	
 • Outdoors session with bacon and eggs 	X	X
	Friday PM 9 - 9:30pm	
 • Booster session • Wind down with beanbags • Headphones provided for relaxing music • Reinforcing stimulus control therapy 	X	X

Participant Time Line

Time Frame for Activity	Screen	Program cycle		
		At recruitment	Weekly	At discharge
Initial screening in handovers by clinical staff	X			
Initial medical assessment for appropriateness	X			
Self-report measures		X	x	X
Sleep Diary			X	
Qualitative evaluation Questionnaire				X
Ward initiatives		X	X	
Retimer™ Light goggles			X	
Actigraphy data		X	X	
Sleep Program groups		x	X	
Psychoeducation about sleep hygiene		X	X	
Program usage		X	X	X
Adverse event monitoring		X	X	X

Study Procedure Risks

1. Skin damage due to photosensitivity
Some medications, notably Chlorpromazine, are known to increase the photosensitivity of the skin. The Program entails exposure to natural and low intensity artificial light, which may cause irritation and minor sunburns.
2. Headache from tightness or poor fit of light spectacles
The Retimer™ light goggle is made from rigid plastic and are not adjustable for size of head. Therefore, it is possible that participants may experience discomfort on the ridge of their nose, or sections of the skin around the auricle which makes contact with the goggle.
3. Discomfort from artificial light
The Retimer light goggle emits light in two different intensity settings, which is projected upwards towards the light. Whilst the light intensity is safe, it may still be a source of discomfort and annoyance to the patient.
4. Sleep disturbance
The Program is an evidence-based intervention aimed to reset and align the circadian rhythm to normal daylight hours. However, there is a risk that the integrated intervention does not improve sleep quality and quantity, or indeed, may worsen them.
5. Psychological harm: wearing a watch which constantly collects data might further enhance persecutory or paranoid ideations in the sub-population of participants who are experiencing psychotic symptoms. However, given the study requires informed consent, the likelihood of a paranoid patient consenting to participate is small.

Given the non-invasive, interactive and patient-driven nature of the intervention, it is expected that participants will have minimal risks in the following domains:

- disclosure of sensitive personal information
- exposure of illegal activity
- economic harm
- discrimination, stigma or other social harm
- devaluation or harassment
- familial distress
- harm to any member of a vulnerable population
- reputational harm

Informed Consent Process

There is a one-stage consent process to entry into the study. The Senior occupational therapist, [name] (investigator in this study) will introduce the study and discuss the main aspects to potential eligible participants in person in the first instance to reduce medical-patient power imbalance.

Participants will receive the study information sheets in hard copy. Research clinicians will discuss the study with participants in light of the information provided to them. The research clinician will obtain written content from patients willing to participate.

A potential participant has one week to consider their participation; however, they may defer that decision up until two weeks prior to their expected discharge date from the HDU - given a meaningful study period is defined as a minimum of two weeks of participation.

Enrolment Procedure

The participant will be enrolled into the study after the informed consent process has been completed and the participant has met all inclusion criteria and none of the exclusion criteria.

Participants need to be inpatient at HDU North (male) in PMBC, Royal Prince Alfred Hospital.

Participants are first identified as potential (candidate) participant by medical/OT/SW/RN from Multi-Disciplinary Team (MDT) meeting, satisfying inclusion and exclusion criteria.

The participant will receive a study enrolment number (Participant ID number), and this will be documented in secure and confidential register, as well as in the medical records.

Capacity

Potential (candidate) participants are clinically assessed for the ability to understand and capacity to give consent. The consultant in the treating team must deem the candidate participant as having capacity to consent; and this must be a consensus impression by the rest of the MDT. Further, it must be verifiable by demonstrated understanding and engagement with the Sleep Program. Mental state is monitored on an ongoing basis as per standard care. In cases where a participant deteriorates or loses capacity to consent and participate altogether: their involvement in the study will cease. This is outlined under *Early Terminations*.

Randomisation Procedure

Not applicable

Adverse Event Reporting

